6.2.4. Imaging Data Repeat Scan and Re-read

For MRI-PDFF and MRE data, if a patient has an analyzable repeat scan, then only repeat scan for that visit will be used for analysis. For MRE data, if a patient has a re-read result, then the re-read result for that visit will be used for analysis.

6.3. Subgroup Analysis of the Efficacy Endpoints

Subgrouping of subjects based on randomization stratification factors will be explored as follows:

- presence of diabetes mellitus
- absence of diabetes mellitus

Descriptive statistics for the above subgroups will be presented for the baseline values, values at each postbaseline visit, change from baseline, and percent change from baseline by visit for MRE and MRI-PDFF.

For each subgroup, the proportion of subjects with at least 30% reduction in MRI-PDFF at Week 12 and the proportion of subjects with at least 15% reduction in MRE at Week 12 will be reported for each treatment group by using a point estimate and 95% CI of the proportion

based on the Clopper-Pearson method. The 95% CI for the difference in proportion between GS-0976 and Placebo will also be provided.

Within each subgroup, the change from baseline of MRI-PDFF and MRE at Week 12 will be analyzed by using an ANCOVA model, with treatment group, and baseline MRI-PDFF or MRE as covariates. For change from baseline, LS means and 95% CIs of LS means will be reported for each treatment group. For treatment differences (GS-0976 – Placebo) of changes from baseline of MRI-PDFF or MRE at Week 12, LS means and 95% CIs will be reported.

Mean (SD) of the observed change from baseline value will be plotted using a line plot by treatment group and visit for subjects from each subgroup.

6.4. Changes From Protocol-Specified Efficacy Analyses

There is no change from protocol specified analysis.

7. SAFETY ANALYSES

7.1. Adverse Events and Deaths

7.1.1. Adverse Event Dictionary

Clinical and laboratory AEs will be coded using the current version of MedDRA. System organ class (SOC), high-level group term (HLGT), high-level term (HLT), preferred term (PT), and lower-level term (LLT) will be provided in the AE dataset.

7.1.2. Adverse Event Severity

Adverse events are graded by the investigator as Grade 1, 2, 3, 4, or 5 according to the Common Terminology Criteria for Adverse Events (CTCAE), Version 4.03, detailed in Appendix 4. The severity grade of events for which the investigator did not record severity will be categorized as “missing” for tabular summaries and data listings. The missing category will be listed in summary presentations.

7.1.3. Relationship of Adverse Events to Study Drug

Related AEs are those for which the investigator selected “Related” on the AE CRF to the question of “Related to Study Treatment.” Relatedness will always default to the investigator’s choice, not that of the medical monitor. Events for which the investigator did not record relationship to study drug will be considered related to study drug for summary purposes. However, by-subject data listings will show the relationship as missing.

7.1.4. Serious Adverse Events

Serious adverse events (SAEs) will be identified and captured as SAEs if AEs met the definitions of SAE specified in the study protocol. Serious adverse events captured and stored in the clinical database will be reconciled with the SAE database from the Gilead Drug Safety and Public Health Department before data finalization.

7.1.5. Treatment-Emergent Adverse Events

7.1.5.1. Definition of Treatment-Emergent Adverse Events

Treatment-emergent adverse events (TEAEs) are defined as 1 or both of the following:

- Any AEs with an onset date on or after the study drug start date and no later than 30 days after permanent discontinuation of study drug
- Any AEs leading to premature discontinuation of study drug.

7.1.5.2. Incomplete Dates

If the onset date of the AE is incomplete and the AE stop date is not prior to the first dosing date of study drug, then the month and year (or year alone if month is not recorded) of onset determine whether an AE is treatment emergent. The event is considered treatment emergent if both of the following 2 criteria are met:

- The AE onset is the same as or after the month and year (or year) of the first dosing date of study drug, and
- The AE onset date is the same as or before the month and year (or year) of the date corresponding to 30 days after the date of the last dose of study drug

An AE with completely missing onset and stop dates, or with the onset date missing and a stop date later than the first dosing date of study drug, will be considered to be treatment emergent. In addition, an AE with the onset date missing and incomplete stop date with the same or later month and year (or year alone if month is not recorded) as the first dosing date of study drug will be considered treatment emergent.

7.1.6. Summaries of Adverse Events and Deaths

Treatment-emergent (TE) AEs will be summarized based on the Safety Analysis Set.

The number and percentage of subjects who experienced at least 1 TEAE will be provided and summarized by SOC, HLT, PT, and treatment group. For other AEs described below, summaries will be provided by SOC, PT, and treatment group.

- TEAEs of Grade 3 or higher (by maximum severity)
- TEAEs of Grade 2 or higher
- All TE treatment-related AEs
- TE treatment-related AEs of Grade 3 or higher (by maximum severity)
- TE treatment-related AEs of Grade 2 or higher
- All TE SAEs
- All TE treatment-related SAEs
- All TEAEs leading to premature discontinuation of study drug
- All TEAEs leading to premature discontinuation of study
- All TEAEs leading to dose temporary interruption of study drug

A brief, high-level summary of AEs described above will be provided by treatment group and by the number and percentage of subjects who experienced the above AEs. All deaths observed in the study will also be included in this summary.

Multiple events will be counted only once per subject in each summary. Adverse events will be summarized and listed first in alphabetic order of SOC and HLT within each SOC (if applicable), and then by PT in descending order of GS-0976 20 mg frequency within each SOC (HLT, if present). For summaries by severity grade, the most severe grade will be used for those AEs that occurred more than once in an individual subject during the study.

In addition to the above summary tables, TEAEs and TE treatment-related AEs will be summarized by PT only for the following, in descending order of GS-0976 20 mg frequencies:

- TE Adverse Events by Preferred Term
- Grade 3 or Higher TEAEs by Preferred Term
- Grade 2 or Higher TEAEs by Preferred Term
- TE treatment-Related AEs by Preferred Term
- Grade 3 or Higher TE treatment-Related AEs by Preferred Term
- Grade 2 or Higher TE treatment-Related AEs by Preferred Term
- All TE SAEs by Preferred Term
- All TE treatment-related SAEs by Preferred Term
- All TEAEs leading to premature discontinuation of study drug by Preferred Term
- All TEAEs leading to premature discontinuation of study by Preferred Term
- All TEAEs leading to temporary interruption of study drug by Preferred Term

In addition, data listings will be provided for the following:

- All AEs, indicating whether the event is treatment emergent
- All AEs of Grade 3 or higher
- All AEs of Grade 2 or higher
- SAEs

- Deaths
- AEs leading to premature discontinuation of study drug
- AEs leading to premature discontinuation of study
- AEs leading to temporary interruption of study drug

7.2. **Laboratory Evaluations**

Laboratory data collected during the study will be analyzed and summarized using both quantitative and qualitative methods. The analysis will be based on values reported in conventional units. When values are below the LOQ, they will be listed as such, and the closest imputed value will be used for the purpose of calculating summary statistics as specified in Section 3.7.

A by-subject listing for laboratory test results will be provided by subject ID number and visit in chronological order for hematology, serum chemistry, and urinalysis separately. Values falling outside of the relevant reference range and/or having a severity grade of 1 or higher according to the CTCAE, Version 4.03 will be flagged in the data listings, as appropriate.

No formal statistical testing is planned.

7.2.1. **Summaries of Numeric Laboratory Results**

Descriptive statistics will be provided by treatment group for each laboratory test listed below:

- Chemistry Panel:
Creatinine, fasting glucose, fasting insulin, eGFR using the Cockcroft-Gault equation, serum creatinine
- Coagulation Panel: INR
- Hematology: white blood cell (WBC), neutrophils, lymphocytes, hemoglobin, platelets

For each laboratory test specified above, the descriptive statistics will be provided as follows:

- Baseline values
- Values at each postbaseline visit
- Change from baseline at each postbaseline visit

Change from baseline to a postbaseline visit will be defined as the postbaseline value minus the baseline value. The mean, median, Q1, Q3, minimum, and maximum values will be displayed to the reported number of digits; SD values will be displayed to the reported number of digits plus 1.

Median (Q1, Q3) of the observed values for albumin, creatinine, glucose, fasting insulin, WBC, neutrophils, lymphocytes, hemoglobin, platelets, INR, and eGFR will be plotted using a line plot by treatment group and visit.

In the case of multiple values in an analysis window, data will be selected for analysis as described in Section 3.8.3.

7.2.2. **Graded Laboratory Values**

The CTCAE, Version 4.03 will be used to assign toxicity grades (0 to 4) to laboratory results for analysis. Grade 0 includes all values that do not meet the criteria for an abnormality of at least Grade 1. For laboratory tests with criteria for both increased and decreased levels, analyses for each direction (ie, increased, decreased) will be presented separately.

7.2.2.1. **Treatment-Emergent Laboratory Abnormalities**

Treatment-emergent laboratory abnormalities are defined as values that increase at least 1 toxicity grade from baseline at any postbaseline time point, up to and including the date of last dose of study drug plus 30 days for subjects who permanently discontinued study drug. If the relevant baseline laboratory value is missing, any abnormality of at least Grade 1 observed within the time frame specified above will be considered treatment emergent.

7.2.2.2. **Treatment-Emergent Marked Laboratory Abnormalities**

Treatment-emergent marked laboratory abnormalities are defined as values that increase from baseline by at least 3 toxicity grades at any postbaseline time point, up to and including the date of the last dose of study drug plus 30 days for subjects who permanently discontinued study drug. If the relevant baseline laboratory value is missing, any Grade 3 or 4 values observed within the timeframe specified above will be considered treatment-emergent marked abnormalities.

7.2.2.3. **Summaries of Laboratory Abnormalities**

Laboratory data that are categorical will be summarized using the number and percentage of subjects in the study with the given response at baseline and each scheduled postbaseline visit.

The following summaries (number and percentage of subjects) for treatment-emergent laboratory abnormalities will be provided by lab test and treatment group; subjects will be categorized according to the most severe postbaseline abnormality grade for a given lab test:

- Graded laboratory abnormalities

- Grade 3 or 4 laboratory abnormalities
- Marked laboratory abnormalities

For all summaries of laboratory abnormalities, the denominator is the number of subjects with nonmissing postbaseline values up to 30 days after last dosing date for the laboratory test of interest.

A by-subject listing of treatment-emergent Grade 3 or 4 laboratory abnormalities will be provided by subject ID number and visit in chronological order. This listing will include all test results that were collected throughout the study for the lab test of interest, with all applicable severity grades and abnormal flags displayed.

7.2.3. Liver-related Laboratory Evaluations

Liver-related abnormalities after initial study drug dosing will be examined and summarized using the number and percentage of subjects who were reported to have the following laboratory test values listed in Section 7.2.3.1 for postbaseline measurements:

The summary will include data from all postbaseline visits up to 30 days after the last dose of study drug. For individual laboratory tests, subjects will be counted once based on the most severe postbaseline values. For both the composite endpoint of AST or ALT and total bilirubin, ALP, INR (as described below), subjects will be counted once when the criteria are met at the same postbaseline visit date. The denominator is the number of subjects in each reporting group (if applicable) in the Safety Analysis Set who have nonmissing postbaseline values of all relevant tests at the same postbaseline visit date.

7.2.3.1. Criteria for Observation of Drug Induced Liver Injury (DILI)

For subjects with ALT (AST) baseline meeting one of the following 2 categories, close observation for DILI should be considered if the subjects meet any of the postbaseline criteria corresponding to each baseline category below.

- 1) For subjects with ALT (AST) below ULN at study baseline AND
 - meeting any of the following postbaseline criteria for liver-related events:
 - ALT (AST) $> 3 \times$ ULN at any time
 - Total Bilirubin $> 2 \times$ ULN
 - ALP $> 3 \times$ ULN
 - INR > 1.5 (except for subjects on anticoagulant therapy)
 - meeting any of the following postbaseline criteria for drug withheld:
 - ALT (AST) $> 3 \times$ ULN and Total Bilirubin $> 2 \times$ ULN

- ALT (AST) $> 3 \times \text{ULN}$ and INR > 1.5 (except for subjects on anticoagulant therapy)
- ALT (AST) $> 5 \times \text{ULN}$
- ALT (AST) $> 8 \times \text{ULN}$

2) For subjects with ALT (AST) greater than or equal to $1 \times \text{ULN}$ at study baseline AND

- meeting any of the following postbaseline criteria for liver-related events :

- ALT (AST) $> 2 \times \text{Baseline}$ at any time
- Total Bilirubin $> 2 \times \text{ULN}$
- ALP $> 3 \times \text{ULN}$
- INR > 1.5 (except for subjects on anticoagulant therapy)

- Meeting any of the following postbaseline criteria for drug withheld:

- ALT (AST) $> 3 \times \text{ULN}$ and Total Bilirubin $> 2 \times \text{ULN}$
- ALT (AST) $> 3 \times \text{ULN}$ and INR > 1.5 (except for subjects on anticoagulant therapy)
- ALT (AST) $> 5 \times \text{ULN}$
- ALT (AST) $> 8 \times \text{ULN}$

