## **7.5. Toxicity Management**

Observation for Drug Induced Liver Injury (DILI):

Although subjects randomized in this study will have baseline liver disease, their hepatic function should not be significantly impaired. However, at baseline, some may have liver biochemistry levels above the upper limit of normal (ULN).

For subjects with ALT and AST below ULN at study start, close observation for DILI (as described below) should be considered in subjects with any of the following criteria (all labs confirmed by repeat testing):

- ALT or AST > 3 x ULN at any time
- Total bilirubin > 2 x ULN
- ALP > 3 x ULN
- INR >1.5 x ULN (except for subjects on anticoagulant therapy)
- Clinical signs or symptoms that are, in the opinion of the investigator, consistent with hepatitis (such as right upper quadrant discomfort, fever, nausea, vomiting, jaundice, rash, or eosinophilia > 5%)

For subjects with ALT or AST between 1 and 5 x ULN at study start, close observation for DILI (as described below) should be considered in subjects with any of the following criteria (all labs confirmed by repeat testing):

- ALT or AST > 2 x baseline at any time
- Total bilirubin > 2 x ULN

- ALP > 3 x ULN
- INR >1.5 x ULN (except for subjects on anticoagulant therapy)
- Clinical signs or symptoms that are, in the opinion of the investigator, consistent with hepatitis (such as right upper quadrant discomfort, fever, nausea, vomiting, jaundice, rash, or eosinophilia > 5%).

Close observation includes:

- Repeating liver biochemistries (ALT, AST, ALP, total bilirubin, INR) within 48 hours
- Obtaining a more detailed history of symptoms and prior or concurrent disease
- Obtaining a history of concomitant drug use (including nonprescription medications and herbal and dietary supplement preparations), alcohol use, recreational drug use, and special diets
- Obtaining a history of exposure to environmental chemical agents
- Ruling out other causes of liver disease as needed (obtain viral hepatitis panel, imaging for evaluation of biliary tract disease, etc. if required in the opinion of the primary investigator)
- Continue to monitor liver biochemistries twice weekly. Frequency can decrease to once a week or less if abnormalities stabilize or study drugs have been discontinued and subject is asymptomatic

During a period of close observation, study drugs can be continued, if desired, at the discretion of the principal investigator.

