However, for all subjects, study drugs should be withheld if any of the following criteria are met:

- ALT or AST > 3 x ULN AND either Total bilirubin > 2 x ULN or INR > 1.5 (in subjects not on anticoagulation)
- ALT or AST > 3 x ULN AND the appearance of fatigue, nausea, vomiting, right upper quadrant pain or tenderness, fever, rash, and/or eosinophilia (>5%)
- ALT or AST > 8 x ULN
- ALT or AST > 5 x ULN for more than 2 weeks

AND

- No other cause for the combination of laboratory abnormalities is immediately apparent (e.g. prolonged INR with warfarin use) important potential causes or contributors to abnormal AST/ALT or total bilirubin values include, but are not limited to:

— Obstructive gall bladder or bile duct disease

- Viral or alcoholic hepatitis (e.g. hepatitis A/B/C/D/E, Epstein-Barr virus, cytomegalovirus, herpes simplex virus, varicella)
- Autoimmune hepatitis
- Concomitant administration of other hepatotoxins, including excessive doses of acetaminophen, drugs that inhibit bilirubin glucuronidation (e.g. indinavir, atazanavir, irinotecan), or herbal or dietary supplements
- Hypoxic or ischemic hepatopathy or congestive hepatopathy in association with significant right-sided heart failure
- Wilson disease
- Progression of malignancy involving the liver (note that metastatic disease to the liver, by itself, should not be used as an explanation for significant AST/ALT elevations)

If study drugs are withheld, they may be reintroduced with approval from the Gilead Medical Monitor.

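### The SAP table of subjects meeting the DILI close-observation criteria does not count exactly the set that protocol 7.5 defines, because its baseline grouping and its INR cut-off differ

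*SAP*

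**What the plan says.** Protocol 7.5 (Toxicity Management) sets the close-observation rule. The first branch reads "For subjects with ALT and AST below ULN at study start" and the second "For subjects with ALT or AST between 1 and 5 x ULN at study start". In the first, the enzyme trigger is either enzyme above 3 x ULN. In the second it is "ALT or AST > 2 x baseline at any time". Both branches share the bilirubin and ALP triggers, the INR trigger "INR >1.5 x ULN (except for subjects on anticoagulant therapy", and a criterion based on signs or symptoms of hepatitis. Both carry the condition "all labs confirmed by repeat testing".

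The separate rule for withholding study drug, later in protocol 7.5, uses an absolute INR: "or INR > 1.5 (in subjects not on anticoagulation".

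SAP 7.2.3.1 presents its list as the criteria for considering close observation. Its first category is introduced by "For subjects with ALT (AST) below ULN at study baseline AND"; the second is ALT (AST) at or above 1 x ULN, with no upper bound. The INR row for liver-related events is "INR > 1.5 (except for subjects on anticoagulant therapy" in both categories. SAP 7.2.3.2 then reports number and percentage by treatment, by ALT (AST) baseline condition and by criterion, with a listing of subjects who met at least one criterion.

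**The concern.** In the protocol the branch belongs to the subject. In the SAP, as ALT (AST) is most naturally read, it belongs to the enzyme. The two agree when both enzymes lie on the same side of ULN at baseline and can disagree when they do not. The INR row differs for every subject not on anticoagulant therapy, unless the ULN is exactly 1.0.

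Safety is the primary endpoint (protocol 8.1.2), and some subjects are expected to start above ULN (protocol 7.5). A reader of the study report would take a table headed by the close-observation criteria as the number who met the protocol's rule. As specified it is a somewhat different number, and it need not match the observation episodes that sites opened.

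**Working it through.** The plan gives no figure to reproduce here, so the check is a comparison of rules, followed by sizes under stated assumptions.

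**1. Enzyme by enzyme.** Take baseline ALT 1.5 and AST 0.6 x ULN, then ALT 1.5 and AST 1.3 x ULN.
- Protocol: second branch, because ALT is raised. AST ratio 1.3 / 0.6 = 2.2 > 2, so the trigger is met (subject to repeat testing).
- SAP: ALT is in the upper category, 1.5 / 1.5 = 1.0, not met. AST is in the lower category, 1.3 is not above 3, not met.

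This reading can only miss subjects. An enzyme that starts below ULN and exceeds 3 x ULN has more than tripled, so it also meets the protocol's doubling trigger.

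**2. Read as ALT or AST.** Take baseline ALT 0.6 and AST 2.0 x ULN, then ALT 0.7 and AST 3.2 x ULN.
- Protocol: second branch. 3.2 / 2.0 = 1.6 and 0.7 / 0.6 = 1.2, not met.
- SAP: ALT below ULN admits the subject to the lower category, and AST 3.2 > 3 counts.

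This reading can only add subjects, because each SAP category then contains the matching protocol branch.

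**3. Grid check of the enzyme triggers.** Baseline ALT and AST each ran from 0.3 to 3.0 x ULN in steps of 0.1 (28 values), and postbaseline values from 0.3 to 6.9 in steps of 0.2 (34 values): 28² x 34² = 906,304 combinations. Of these, 2 x 7 x 21 x 34² = 339,864 have discordant baselines.

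| Reading of ALT (AST) | Protocol met, SAP not | SAP met, protocol not |
|---|---|---|
| Enzyme by enzyme | 50,274 | 0 |
| ALT or AST | 0 | 8,400 |

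These are counts of grid cells, not expected frequencies. They confirm the direction of each error. All 339,864 discordant combinations belong to both SAP categories.

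**4. INR observation row.** The documents give no INR ULN. The protocol cut-off is 1.5 x ULN; the SAP's is fixed at 1.5.

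| Assumed ULN | Protocol cut-off | Counted by the SAP only |
|---|---|---|
| 1.0 | 1.50 | none |
| 1.1 | 1.65 | above 1.50, up to 1.65 |
| 1.2 | 1.80 | above 1.50, up to 1.80 |
| 1.3 | 1.95 | above 1.50, up to 1.95 |

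**5. How many subjects are discordant.** The documents give no baseline enzyme distribution. Assume bivariate lognormal values with medians 1.0-1.4 x ULN (ALT) and 0.8-1.1 x ULN (AST), between-subject CV 50% and correlation 0.6-0.8 on the log scale. The discordant share is P(ALT < ULN) + P(AST < ULN) - 2 P(both < ULN). Over the corners of these ranges it runs from 0.21 (medians 1.0 and 1.1, correlation 0.8) to 0.48 (1.4 and 0.8, correlation 0.6): about 27 to 60 of 125.

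**6. Protocol-only triggers from noise.** Assume the enzyme that was normal at baseline has a stable true level and independent lognormal within-subject error at baseline and at five later visits (Weeks 1, 4, 8, 12 and Follow-Up). Treat confirmation as one independent repeat that also exceeds twice baseline.

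| Within-subject CV | Any visit > 2 x baseline | Confirmed by a repeat |
|---|---|---|
| 20% | 0.027 | 0.003 |
| 25% | 0.086 | 0.016 |
| 30% | 0.160 | 0.040 |

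The expected number runs from 27 x 0.003 = 0.1 to 60 x 0.040 = 2.4, so about 0 to 2 subjects.

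**The case against.** The strongest defence is that ALT (AST) is ordinary shorthand for two parallel displays, one by ALT and one by AST. Within each display every subject is either below ULN or not, so the strata are disjoint and nobody is counted twice. That stands as a possible intention. A reader might infer that the baseline strata necessarily overlap; the documents do not support that, because the overlap arises only if the displays are not kept separate. The SAP does not say which is meant. Separate displays would still miss the case in step 1.

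A reader might also infer that the table fails to count those who met the protocol rule. That goes too far: many subjects meet both rules, and the INR difference only adds subjects when the ULN exceeds 1.0. Nor does the SAP's absolute INR come from nowhere, since the protocol uses it for withholding.

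A third inference would be that SAP 7.7, which declares no deviation from the protocol's safety analyses, is false. Protocol 8.6.3 specifies numeric summaries and graded abnormalities and no DILI table. This table is a SAP addition, so no protocol-specified analysis is contradicted.

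Finally, the table is descriptive. Graded ALT and AST abnormalities are summarised separately, and Grade 3 or 4 results are listed, whatever the grouping. No test or stopping rule in the documents uses this table. That limits the consequence but does not make the count right: the DILI listing covers only subjects who met the SAP's own criteria, so a protocol-only case is absent from it.

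**Conclusion.** The point holds in a limited form. The SAP reports subjects meeting the close-observation criteria, yet under either reading of ALT (AST) its rule selects a different set from protocol 7.5. A discordant subject has no single SAP baseline category, so bilirubin, ALP and INR events can appear under both categories unless separate ALT and AST displays are intended. The INR observation row differs between the documents and, for a ULN above 1.0, over-counts relative to the protocol.

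These differences are plain in the text and need no assumption. The sizes do: 21-48% discordant rests on the assumed distributions, and about 0 to 2 noise-only triggers rests on the assumed error model and independent repeats. Counting unconfirmed single values would give a larger figure, but such values do not meet the protocol rule. True enzyme rises are not included in that figure.

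The impact is one descriptive safety table and its listing. It should be corrected because safety is the primary endpoint and the correction is cheap.

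**What to change.** Before database lock:

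1. In SAP 7.2.3.1 and 7.2.3.2, derive one baseline flag per subject (both enzymes below ULN, or either at or above ULN) and apply it to every row. State how a baseline above 5 x ULN is handled, since the protocol's second branch stops there and the SAP's does not.
2. Keep enzyme-specific displays, if wanted, as a labelled supplement, with ALT and AST shown separately.
3. Reconcile the INR observation criterion between the two documents. Which threshold applies is for the sponsor to settle; this review does not choose.
4. Regrouping alone will not reproduce the protocol's set, because the SAP list also leaves out repeat-test confirmation and the signs-and-symptoms criterion. Either reconcile these too, or label the table as laboratory-only and unconfirmed.

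The cost is SAP wording, one derived variable and minor table programming. No new data are needed for items 1 and 2 or for the labelling option in item 4.

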#### **4.3. Exclusion Criteria**

Subjects who meet *any* of the following exclusion criteria will not be randomized in this study.

- 1) Pregnant or lactating females; lactating females must agree to discontinue nursing before the study drugs are administered;
- 2) ALT > 5 x ULN;
- 3) Other causes of liver disease including autoimmune, viral, and alcoholic liver disease;
- 4) Cirrhosis of the liver as defined by any of the following:
  - a) Cirrhosis on historical liver biopsy (e.g. NASH CRN classification stage 4 or equivalent);
  - b) Evidence of cirrhosis on liver imaging (e.g. ultrasound, CT, or MRI) including a nodular liver surface, splenomegaly, or portal venous collaterals;
  - c) Prior history of decompensated liver disease, including ascites, hepatic encephalopathy or variceal bleeding;
  - d) Screening FibroSURE/FibroTest®  $\geq 0.75$ , unless a historical liver biopsy within 12 months of Screening does not reveal cirrhosis. In patients with Gilbert's syndrome or hemolysis, FibroSURE/FibroTest® will be calculated using direct bilirubin instead of total bilirubin.
- 5) History of liver transplantation;
- 6) Weight reduction surgery in the 2 years prior to Screening or planned during the study (weight reduction surgery is disallowed during the study);
- 7) History of intestinal resection or malabsorptive condition that may limit the absorption of GS-0976. Prior cholecystectomy and appendectomy are permitted

- 8) BMI < 18 kg/m^2;
- 9) INR > 1.2, unless on anticoagulant therapy;
- 10) Total bilirubin > 1 x ULN, except with diagnosis of Gilbert's syndrome;
- 11) Chronic hepatitis B (HBsAg positive);
- 12) Chronic hepatitis C (HCV Ab and HCV RNA positive). Subjects cured of HCV infection less than 2 years prior to the Screening visit are not eligible.
- 13) HIV Ab positive;
- 14) Alcohol consumption greater than 21 oz/week for males or 14 oz/week for females (1oz/30mL of alcohol is present in 1 12oz/360mL beer, 1 4oz/120mL glass of wine, and a 1 oz/30 mL measure of 40% proof alcohol);
- 15) Positive urine screen for amphetamines, cocaine or opiates (i.e. heroin, morphine) at Screening. Subjects on stable methadone or buprenorphine maintenance treatment for at least 6 months prior to Screening may be included in the study. Subjects with a positive urine drug screen due to prescription opioid-based medication are eligible if the prescription and diagnosis are reviewed and approved by the investigator;

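### The SAP liver table counts raised total bilirubin without reference to baseline, so Gilbert's subjects with unchanged values can appear as meeting its close-observation or drug-withheld criteria

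*SAP*

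**What the plan says.** Protocol 4.3, exclusion 10, rules out "Total bilirubin > 1 x ULN, except with diagnosis of Gilbert's syndrome". No upper limit is given for those exempted. Exclusion 4d says that, in Gilbert's syndrome or hemolysis, the FibroTest score "will be calculated using direct bilirubin instead of total bilirubin". Exclusion 2 sets the ALT ceiling at 5×ULN. The closing note to 4.3 lets the Medical Monitor approve subjects whose laboratory values fall outside the limits.

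SAP 7.2.3.1 says that "close observation for DILI should be considered if the subjects meet any of the postbaseline criteria". In both baseline ALT (AST) categories the liver-related-event list contains "Total Bilirubin $> 2 \times$ ULN", and the drug-withheld list contains "ALT (AST) $> 3 \times$ ULN and Total Bilirubin $> 2 \times$ ULN". The INR entries carry an exemption, "except for subjects on anticoagulant therapy", and in the raised-baseline category the first ALT (AST) entry is a multiple of baseline. The bilirubin entries have neither adjustment.

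Under SAP 7.2.3, for single tests, "subjects will be counted once based on the most severe postbaseline values"; combined criteria must be met on the same visit date. SAP 7.2.3.2 tabulates the counts by treatment and baseline ALT (AST) category and lists every subject who meets a criterion.

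**The concern.** The trial deliberately admits some subjects whose total bilirubin may already exceed a threshold that the liver table later treats as a postbaseline finding. The table cannot separate a pre-existing elevation that persists from a rise on treatment.

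This matters because the primary endpoint is safety (Protocol 8.1.2) and these rows will be small. Apart from Medical Monitor approvals, a subject without Gilbert's enters at or below 1×ULN, so total bilirubin must more than double to pass 2×ULN. One or two unchanged Gilbert's subjects could therefore supply much of what the bilirubin rows show, and a reader of the table would not know it.

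**Working it through.** The plan gives no figure to reproduce. The check is a reading of the rules, followed by an illustration of size.

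**1. Can an unchanged subject be counted?** Take a Gilbert's subject with total bilirubin above 2×ULN and ALT between 3 and 5×ULN at baseline, both unchanged on study.

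- Entry: exclusion 10 does not apply, and ALT is within the exclusion 2 limit.
- Bilirubin-alone row: the postbaseline value is above 2×ULN, so the subject is counted.
- Combined drug-withheld row: ALT is above 3×ULN and bilirubin above 2×ULN on one date, so the subject is counted.
- ALT row in the raised-baseline category: unchanged ALT is 1× baseline, not above 2×, so the subject is not counted.
- Treatment-emergent graded bilirubin (SAP 7.2.2.1): a rise of at least one grade is required, so the subject is not counted.

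The combined row can be met without change only in the raised-baseline category. A subject with baseline ALT below ULN needs a real ALT rise to exceed 3×ULN. The bilirubin-alone row can be met without change in either category.

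**2. What the SAP leaves out of Protocol 7.5.** The protocol uses the same 2×ULN threshold, also without a Gilbert's exception. It adds two safeguards: the close-observation laboratory values are confirmed by a repeat test, and withholding applies only when no other explanation is readily evident. The SAP rows include neither. A subject for whom the protocol would not call for withholding can therefore appear under a drug-withheld criterion.

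**3. Size, bilirubin-alone row.** From the SAP: 50 + 50 = 100 active subjects and 25 placebo. Assumed, not in the documents: a share g = 2% to 10% of subjects has Gilbert's, and a share h = 10% to 50% of those exceeds 2×ULN at some postbaseline visit. With q = g × h:

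- expected count = 125q
- P(at least one) = 1 − (1 − q)^125
- P(at least one on active, none on placebo) = [1 − (1 − q)^100] × (1 − q)^25

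| g, h | q | Expected of 125 | P(at least one) | P(active only) |
|---|---|---|---|---|
| 2%, 10% | 0.002 | 0.25 | 0.22 | 0.17 |
| 5%, 25% | 0.0125 | 1.56 | 0.79 | 0.52 |
| 10%, 50% | 0.05 | 6.25 | 0.998 | 0.28 |

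One subject is 1/50 = 2% of an active arm, 1/100 = 1% of pooled active and 1/25 = 4% of placebo, before any missing data or the split by baseline ALT (AST).

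**4. Combined row.** A figure would also need the share with ALT or AST above 3×ULN on the same date. The documents do not give it, so none is offered. The count cannot exceed that for bilirubin alone.

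**The case against.** Several objections stand.

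- A reader might infer that Gilbert's subjects are recorded as having drug-induced liver injury. They are not: the SAP counts subjects who meet observation or withholding criteria and lists them. Nothing is adjudicated.
- A reader might infer that the SAP departs from the protocol, or that the documents define abnormal bilirubin in two conflicting ways. The 2×ULN threshold, the anticoagulant exemption and the baseline-referenced ALT/AST rule all come from Protocol 7.5. An entry limit, a FibroTest input and a monitoring trigger are different uses, and the protocol gives no reason for using direct bilirubin in FibroTest.
- The active-only probabilities might be read as bias against GS-0976. They mainly reflect 4:1 allocation and would apply to any rare event unrelated to treatment. If k such subjects occur, all fall on active with probability about 0.8^k: 80%, 64% and 51% for k = 1, 2 and 3. The expected percentage is equal in every arm and no formal testing is planned.
- Entry is not wholly open. Exclusion 19 lets the investigator exclude a laboratory abnormality that could impair assessment of the results.
- Removing Gilbert's subjects from the bilirubin rows could hide a genuine combined rise, so that remedy is not recommended.

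The graded table and the listing help only in part. In SAP Appendix 4, Grade 2 bilirubin runs from above 1.5 to 3.0×ULN, so that table does not show crossings of 2×ULN, and it has no combined ALT-plus-bilirubin row. As specified, the listing carries no Gilbert's marker.

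**Conclusion.** The point holds as a gap in the display. SAP 7.2.3.1 can count a subject with no change from baseline in the bilirubin row and, where baseline ALT is between 3 and 5×ULN, in the combined row. That much follows from the text alone.

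How often it will happen is unknown. The range of 0.25 to 6.25 subjects rests entirely on assumed prevalences and is too wide to establish a material effect. The number is probably small, but few other subjects are expected in these rows. The result is noise and possible misreading of a descriptive safety table. The documents do not support a claim of bias between arms or of misdiagnosed liver injury. The improvement is worth making because it is cheap and removes nothing.

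**What to change.** - Keep the existing rows in SAP 7.2.3.1 and 7.2.3.2, with all subjects in them.
- Add companion rows for the bilirubin criterion and for the combined ALT (AST)-plus-bilirubin criterion, counting only subjects who did not already meet the same criterion at baseline as defined in SAP 3.8.2. Count subjects with a missing baseline, as SAP 7.2.2.1 already does for graded abnormalities. These rows need no Gilbert's flag.
- Alternatively or in addition, show direct bilirubin over time for Gilbert's subjects. Direct bilirubin is already in the chemistry panel (Protocol 6.8.1). This also helps with a subject just below 2×ULN at baseline who drifts just above it, whom the companion row would still count.
- Set the Gilbert's flag before unblinding and mark flagged subjects in the 7.2.3.2 listing. SAP 5.3 leaves medical history uncoded, so the flag must be built by hand.
- State in a table footnote that the rows do not apply the protocol's repeat-test or alternative-cause conditions.

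The cost is a manual flag, one or two extra rows and a few sentences. If the SAP is already final, its Introduction provides for documenting the change in the study report.

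Separately, the sponsor should reconcile Protocol 4.3, exclusion 10, with the bilirubin criteria in Protocol 7.5. No clinical rule is proposed here.
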